## **11.1 Documenting Serious Adverse Events**

All SAEs should be submitted within 24 hours of the Investigator becoming aware of the event.

Only SAEs associated with study assessments and/or study conduct will be collected using the Safety Information Collection Form..

When an SAE occurs, it is the responsibility of the Investigator to review all documentation (e.g., hospital progress notes, laboratory and diagnostic reports) pertaining to the event. The Investigator will then record all relevant information regarding an SAE on the appropriate form(s).

The Investigator should not send photocopies of the subject's medical records to Indivior in lieu of completion of the Safety Information Collection Form. However, there may be cases where copies of medical records are requested by Indivior or designated representative. In this instance, all subject identifiers, with the exception of subject number, will be redacted on the copies of the medical records prior to submission to Indivior.

The Investigator will attempt to establish a diagnosis of the event based on signs, symptoms, and/or other clinical information. In such cases, the diagnosis will be documented as an AE or SAE and not the individual signs/symptoms.

## **11.2 Reporting Serious Adverse Events**

### **11.2.1 Investigator Reporting of Serious Adverse Events**

Once the Investigator determines that an event meets the protocol definition of an SAE, the SAE will be reported to Indivior (or designated representative) by the Investigator (or designee) within 24 hours from first being aware of the event by completing the appropriate portion of the eCRF(s) and the Safety Information Collection Form. Any follow-up information on a previously reported SAE will also be reported to Indivior within 24 hours by updating the appropriate eCRF(s) or Safety Information Collection Form.

Where additional information is needed or expected, the Investigator will not wait to receive all information before reporting the event to Indivior. The Investigator must provide an assessment of causality at the time of the initial report as described in Section 10.1.3 of the protocol.

The Safety Information Collection Form should be completed and submitted to Indivior Pharmacovigilance via email or fax:

Email: [contact]  
[contact]  
Indivior  
[name]

[name]

### **11.2.2 Regulatory Reporting Requirements for Serious Adverse Events**

Prompt receipt of notifications of SAEs to Indivior or designated representative from Investigators is essential in ensuring that legal obligations and ethical responsibilities regarding the safety of subjects are met.

Indivior has a legal responsibility to notify both the local regulatory authority and other regulatory agencies about the safety of SUBLOCADE. Indivior or designated representative will comply with country-specific regulatory requirements pertaining to safety reporting to Regulatory Authorities, IRBs/ECs and Investigators.

### **11.2.3 Overdose**

This is an observational study with no drug intervention.

## **12 PREGNANCY**

Women of childbearing potential will undergo urine pregnancy tests at each visit. Pregnancy prior to or during the study will not lead to discontinuation. At the time of informed consent, women who are or could become pregnant will also be asked to allow the Sponsor to follow their pregnancy for up to 2 years post-partum. If subjects do not consent to allow their pregnancy to be followed, they can still participate in the study.

If a subject is pregnant and tests negative for buprenorphine and/or norbuprenorphine on quantitative UDS at Visit 1, no further follow-up will be required from the Sponsor on their pregnancy.

In the case of pregnancy, the Investigator or designee will notify Indivior Pharmacovigilance by completing the Safety Information Collection Form within 1 business day. Follow-up information will also be reported via the Safety Information Collection Form.

The Safety Information Collection Form should be completed and submitted to Indivior Pharmacovigilance via email or fax:

Email: [contact]  
[contact]  
Indivior  
[name]  
[name]

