### **Measures of Interest:**

[figure not shown]
The following PK assessments will be performed at each visit of Part A or Part B:

- Collection of a blood sample for the determination of buprenorphine and norbuprenorphine concentrations in plasma;
- Collection of a urine sample:
  - Aliquots (primary and back-up) will be sent to the bioanalytical laboratory for the determination of free buprenorphine and free norbuprenorphine concentrations in urine.
  - Additional aliquots will be prepared and sent to the diagnostic laboratory who will perform 3 analyses: 1) qualitative UDS for buprenorphine; 2) quantitative UDS for buprenorphine, norbuprenorphine and naloxone (quantifiable concentrations of buprenorphine and/or norbuprenorphine on this assessment will indicate a positive result); and 3) determination of creatinine concentration in urine.

Clinical assessments will include a qualitative UDS for opioids plus self-reported use of illicit buprenorphine.

Safety will be assessed based on adverse events (including serious adverse events) associated with study assessments and/or study conduct. Concomitant medications will also be collected.

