## 4.3 Duration of Treatment

This is an observational study with no drug intervention.

Subjects will participate in the study for a maximum study duration of 2 months (+2 weeks).

The total duration of the study for each subject will be as follows:

- If, at Visit 1 (Part A), the subject achieves a negative result for both buprenorphine and norbuprenorphine quantitative UDS, regardless of naloxone result, the duration of his or her participation will be 1 day.
- For subjects who participate in Part B, if the subject completes both visits in Part B, the maximum duration of his or her study participation would be 2 months (+2 weeks).

Based on ongoing review of the data, the Sponsor reserves the right to modify the duration of the study at any time.

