### **5.4 Part B Continuation Criterion**

Results on the quantitative UDS performed at Visit 1 will determine enrolment in Part B:

- Subjects who provide a quantifiable (i.e., positive) result for buprenorphine and/or norbuprenorphine and a non-quantifiable (i.e., negative) result for naloxone will continue into Part B of the study if Part B is still open to enrolment.
- Subjects who achieve negative results for both buprenorphine and norbuprenorphine quantitative UDS (irrespective of naloxone result) at Visit 1 will conclude their study participation, as will subjects who achieve a positive result for buprenorphine and/or norbuprenorphine and a positive result for naloxone on the quantitative UDS performed at Visit 1.

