#### 13.1 DESCRIPTIVE ANALYSIS

The number and percentage of subjects with negative and positive results for buprenorphine on the qualitative UDS will be summarized for FAS Part A at Visit 1 and for FAS Part B across Visits 1, 2 and 3. Qualitative UDS results for opioids other than buprenorphine will be summarized in a similar way.

The number and percentage of subjects with negative results for **both** buprenorphine and norbuprenorphine based on quantitative UDS or free drug concentrations will be summarized for FAS Part A at Visit 1 and for FAS Part B across Visits 1, 2 and 3. Negative and positive results for each analyte will also be summarized (buprenorphine, norbuprenorphine and naloxone for quantitative UDS; buprenorphine and norbuprenorphine for free drug concentrations). A negative result will be any concentration below the lower limit of quantification (LLOQ). A positive result will be any quantifiable concentration.

As for urine, the number and percentage of subjects with negative results for **both** buprenorphine and norbuprenorphine concentrations in plasma will be summarized for FAS Part A at Visit 1 and for FAS Part B across Visits 1, 2 and 3. Negative and positive results for each analyte (buprenorphine, norbuprenorphine) will also be summarized. A negative result will be any concentration below the LLOQ. A positive result will be any quantifiable concentration.

For all above tables, missing data will not be imputed. For Visits 2 and 3, data associated with the reported use of illicit buprenorphine at the visit or the use of prescribed buprenorphine within 3 weeks of the assessment will be excluded from all the above summary statistics calculation for that visit only. Those excluded data, if any, will be indicated in the listings. With respect to Visit 1, no data should be excluded since meeting the exclusion criteria infers that there was no use of prescribed or illicit opioid use within 3 weeks prior to the Screening visit.

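### Protocol Section 12 waives Sponsor pregnancy follow-up when either analyte is negative at Visit 1, whereas the other subject-level rules on this test need both negative

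*Protocol*

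**What the plan says.** Protocol Section 12 asks women who are or could become pregnant to let the Sponsor follow the pregnancy for up to 2 years post-partum; refusal does not bar participation. It then sets a waiver. If a pregnant subject "tests negative for buprenorphine and/or norbuprenorphine on quantitative UDS at Visit 1", "no further follow-up will be required from the Sponsor on their pregnancy". The next paragraph requires the Investigator to notify pharmacovigilance within 1 business day and adds: "Follow-up information will also be reported via the Safety Information Collection Form". Neither of those duties depends on the urine drug screen (UDS) result.

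Elsewhere the same Visit 1 test is handled as follows:

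- Protocol 4.3 limits participation to 1 day if "the subject achieves a negative result for both buprenorphine and norbuprenorphine quantitative UDS, regardless of naloxone result".
- Protocol 5.4 ends participation for "Subjects who achieve negative results for both buprenorphine and norbuprenorphine quantitative UDS (irrespective of naloxone result) at Visit 1". Footnote b of the Schedule of Events says the same in Protocol Appendix 1 and SAP Appendix 1.
- Protocol 5.4 sends on to Part B, subject to a negative naloxone result and an open place, "Subjects who provide a quantifiable (i.e., positive) result for buprenorphine and/or norbuprenorphine".
- The Synopsis, under Measures of Interest, defines the test outcome: "quantifiable concentrations of buprenorphine and/or norbuprenorphine on this assessment will indicate a positive result".
- SAP 13.1 treats a concentration below the LLOQ as negative. It tabulates each analyte separately as well as the count of subjects negative on both.

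**The concern.** *And/or* is inclusive. Attached to a positive finding it means that either analyte is enough, which is how Section 5.4 and the Synopsis use it. Attached to a negative finding it also means that either is enough, and that reverses the protection: a woman with one quantifiable analyte meets the waiver condition because the other is below the LLOQ.

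Followed as written, the sentence relieves the Sponsor of following a pregnancy in a subject who still has measurable drug or metabolite at Visit 1. Since the waiver turns on a drug test, follow-up appears to be tied to exposure. That is an inference, because neither document states the waiver's purpose. If it is right, the wording releases some of the pregnancies the provision was meant to keep.

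**Working it through.** The plan gives no figure to reproduce on this point. The check is a comparison of rules over every possible result.

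**Inputs.** Let B = 1 if buprenorphine is quantifiable on the Visit 1 quantitative UDS and 0 if it is below the LLOQ; let N be the same for norbuprenorphine. The meaning of 0 and 1 follows SAP 13.1 and Protocol 5.4.

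**Rules.**

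- Waiver as worded (Protocol 12): B = 0 or N = 0.
- Both-negative rule (Protocol 4.3, 5.4 and footnote b in both appendices): B = 0 and N = 0.
- Positive test (Synopsis, Measures of Interest): B = 1 or N = 1.

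**All four patterns.**

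| B | N | Test positive (Synopsis) | Waiver as worded | Waiver under both-negative rule |
|---|---|---|---|---|
| 1 | 1 | yes | no | no |
| 1 | 0 | yes | **yes** | no |
| 0 | 1 | yes | **yes** | no |
| 0 | 0 | no | yes | yes |

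**Result.** The wording of Section 12 waives follow-up in 3 of 4 patterns and the both-negative rule in 1 of 4. The difference, 3 − 1 = 2, is the two patterns with exactly one quantifiable analyte. In each of them the Synopsis calls the test positive.

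**Logic.** The opposite of (B = 1 or N = 1) is (B = 0 and N = 0). The waiver is therefore the complement of the positive definition only if it uses *both*. Negating the results while keeping *and/or* gives a different set, which overlaps the positive one in those two rows.

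**What happens to a woman in those two rows.** If her naloxone result is negative and Part B is open, Section 5.4 takes her into Part B as a positive subject. She then has further urine, blood and pregnancy tests at Visits 2 and 3. Section 12, on the same Visit 1 result, has already released the Sponsor from following her pregnancy. Naloxone enters neither the waiver nor the both-negative rule, so it does not change the table.

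**The case against.** The strongest reply is that the conflict depends on the level at which *negative* is read. Taken analyte by analyte, Section 12 does not classify the test at all. It sets a condition for a waiver, and nothing says that condition must mirror the one for leaving the study. Taken at the level of the test, the Synopsis already settles the matter: with either analyte quantifiable the test is positive, so such a woman has not tested negative. On that view the text is loose but can be resolved.

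The second half of this has some force, and a careful reader may well reach the intended meaning. But Section 12 names the analytes and joins them with *and/or*, which points to the analyte-level reading. It does not refer to the Synopsis, and the Synopsis parenthesis is not repeated in the matching list in Protocol 8.2.3. Someone who consults only the pregnancy section sees only the looser rule. As for a deliberate difference, neither document gives a reason for one, and it would waive follow-up even where buprenorphine itself is quantifiable.

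Four further points stand and limit the weight of the finding:

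- The comparators are essentially one participation rule stated in four places, not four independent rules.
- The waiver is permissive. It removes a requirement on the Sponsor and forbids nothing, and the Investigator's notification and follow-up reporting continue.
- The effect needs a subject who is pregnant, has agreed to follow-up and has discordant analytes, among approximately 60 male or female subjects.
- Counts of logical patterns say nothing about how often those patterns occur.

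**Conclusion.** The concern holds, as a minor point. Section 12 as written waives Sponsor follow-up in two result patterns that the protocol treats as positive, and neither document corrects it. The likeliest explanation is that the connective of the positive rule was carried into a negative sentence.

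The number of women affected cannot be derived and may be none. The conclusion rests on the ordinary inclusive meaning of *and/or* and on reading *negative* per analyte, as SAP 13.1 does for its tables. It rests on the protocol and SAP alone; the consent form's wording on pregnancy follow-up was not available. Eligibility, sampling, the population PK model, the descriptive PK analyses and the primary endpoint are unaffected.

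**What to change.** In Protocol Section 12, change the waiver condition to *negative for both buprenorphine and norbuprenorphine*. The waiver then applies to 1 of the 4 patterns, is the exact complement of the Synopsis definition of a positive test, and agrees with Sections 4.3 and 5.4 and with footnote b in both appendices. Nothing else needs to change.

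The edit is one phrase, with no effect on visits, samples or analyses. Under Protocol Section 17 a permanent change still needs IRB approval before it is implemented, and submission to the regulatory authorities. It could reasonably go in with the next amendment made for another reason.

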## **13 DATA MANAGEMENT**

### **13.1 Data Collection and Management**

Data will be entered into the eCRF and will be combined with other data captured centrally outside of the eCRF into a validated system. Clinical data will be managed in accordance with the data management plan to ensure that the integrity of the data is maintained. Adverse events, medical history and indication for concomitant medications will be coded using the Medical Dictionary for Regulatory Activities (MedDRA). Concomitant medications will be coded using the World Health Organization (WHO) Drug Dictionary. The eCRFs (including queries and audit trails) will be retained by Indivior. An electronic copy of the eCRF will be sent to the Investigator to maintain for their records. Per Indivior standards and procedures, subject identifiers will not be collected or transmitted to Indivior. Data collection will be completed according to the study plans.

#### **13.1.1 Database Quality Assurance**

The eCRFs will be reviewed and checked for omissions, apparent errors, and values requiring further clarification using computerized and manual procedures. Data queries requiring clarification will be generated and addressed by the investigational site. Only authorized personnel will make corrections to the eCRFs, and all corrections will be documented in an audit trail.

#### **13.1.2 Source Documents**

The Investigator is responsible for the quality of the data recorded in the eCRFs. The data recorded should be a complete and accurate account of the subject's record collected during the study.

Study data are not to be gathered directly onto the eCRF but must be gathered onto primary source documents at the clinical site. Completion of source documents will precede the completion of the eCRF. Source documents may be electronic, hard copy, or a combination of both and are defined as the results of original observations and activities of a clinical investigation. Source documents will include, but are not limited to, progress notes, electronic data, Screening logs, and recorded data from automated instruments. All source documents pertaining to this study will be maintained by the Investigator and made available for direct inspection by the authorized study personnel.

## 14 STATISTICS

### 14.1 General Procedures

This section describes sample size determination, analysis populations, and planned analyses for PK and safety measures.

Summary statistics on continuous and categorical variables will be calculated when applicable. Continuous variables will be summarised using descriptive statistics such as mean, standard deviation, median, minimum, and maximum. Categorical variables will be reported as frequency counts (including number missing) and the percentage of subjects in corresponding categories. Individual subject data will be presented by subject in data listings. Data listings will include all data collected from the initial Screening visit to the end of the study for all subjects enrolled. A Statistical Analysis Plan (SAP) will be prepared after the protocol is approved and before database lock occurs. The SAP will provide further details regarding analysis. Additional unplanned analyses may be required after all planned analyses have been completed. Any deviations from the analyses described below will be outlined in the SAP. Any unplanned analyses will be clearly identified in the CSR.

No formal statistical testing (p-values, confidence intervals) will be computed due to small sample size.

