### 14.2 Sample Size

The sample size is based on practical considerations and no statistical power is calculated. Approximately 60 subjects will be enrolled in Part A. This number of subjects is expected to provide a reasonable description of the distribution of plasma and urine concentration data in the overall population over the timeframe investigated (i.e., 12 to 36 months post the last SUBLOCADE injection), given the low-moderate interindividual variability (~30%) observed for SUBLOCADE PK in previous studies. The number of subjects to be enrolled in Part A is also limited by the availability of patients who received at least 2 SC injections of SUBLOCADE in Phase III studies and who remain in the time window targeted for enrolment in the current study. A maximum of 30 Part A subjects will proceed to Part B; it is anticipated that approximately 30 subjects will be sufficient to address the objectives for Part B. The final number of subjects will depend on results from quantitative buprenorphine UDS in Part A. Data will be reviewed on an ongoing basis.

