### **6.2 MULTIPLE COMPARISONS**

No statistical tests are performed for this study and thus no multiple comparisons are performed.

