## 13.2.6 Simulations

Simulations will be conducted using the final model to predict long-term buprenorphine plasma exposure after stopping SUBLOCADE treatment (6 injections of 300 mg or 2 injections of 300 mg followed by 4 injections of 100 mg).

The distribution of predicted buprenorphine plasma concentrations will be summarized at each month over at least 36 months post last SUBLOCADE injection in the simulation

study. The percentage of subjects predicted to fall below the limit of quantification will be calculated at each month. Also, the distribution of times during which buprenorphine plasma concentrations stay above the lower limit of quantification following the last dose of SUBLOCADE will be provided.

Additional simulation studies may be conducted as needed.

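### Small sample size is given as the reason to omit confidence intervals, so the Part A percentages carry no measure of precision and the model-predicted percentages are not stated to carry parameter uncertainty

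*Protocol*

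**What the plan says.** Protocol 14.1 puts p-values and confidence intervals in one class and drops both: "No formal statistical testing (p-values, confidence intervals) will be computed due to small sample size". Protocol 14.2 adds: "The sample size is based on practical considerations and no statistical power is calculated". The planned numbers are: "Approximately 60 subjects will be enrolled in Part A", and "A maximum of 30 Part A subjects will proceed to Part B".

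The SAP does not repeat the bar on intervals, but it does not lift it. SAP 6.2 reads: "No statistical tests are performed for this study and thus no multiple comparisons are performed". SAP Section 6 presents categorical data as number and percentage. For Visit 1, SAP 13.1 follows that format: "The number and percentage of subjects with negative and positive results for buprenorphine on the qualitative UDS will be summarized for FAS Part A". The quantitative UDS, free-drug and plasma results likewise "will be summarized for FAS Part A at Visit 1 and for FAS Part B across Visits 1, 2 and 3". SAP Section 17 declares one change from the protocol, the definition of the Full Analysis Set.

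On the model side, SAP Section 16 plans standard errors of the final estimates by importance sampling. SAP 13.2.4 uses precision of estimates to choose between models, and SAP 13.2.5 plans visual predictive checks. SAP 13.2.6 then simulates from the final model: "The percentage of subjects predicted to fall below the limit of quantification will be calculated at each month". It also reports the distribution of time above LLOQ. It does not mention uncertainty in the parameters behind those outputs.

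**The concern.** The reason given does not support the rule. A test asks whether a hypothesis can be rejected, and doing none is reasonable in a descriptive observational study. An interval says how far an estimate may lie from the population value. That matters most when the sample is small, and the exact binomial method needs no minimum size.

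The percentages are also meant to carry an inference. Protocol 1.3 says Part A will inform the percentage of positive and negative urine samples over the 12 to 36 month period and describe the distribution in the overall population. The stated intent is guidance to patients and physicians. As the sample size has no precision calculation behind it, neither document tells a reader how exact a percentage from about 60 subjects will be.

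A related gap affects the simulations. A distribution across simulated subjects shows how patients differ from one another. It does not show how far the predicted percentage itself could move because k64, k36, their variances and CL are estimated. The second quantity is needed to judge a figure such as the share still quantifiable at 36 months.

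**Working it through.** The plan gives no power, alpha or precision figure, so there is none to reproduce.

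**Part A percentages**

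Inputs: n = 60 (Protocol 14.2). The observed proportion is an assumption, since the documents give no expected rate, so a range is shown.

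Exact (Clopper-Pearson) two-sided 95% limits for x positives out of n: the lower limit is the 2.5% quantile of Beta(x, n − x + 1), and the upper limit is the 97.5% quantile of Beta(x + 1, n − x). For x = 0 the upper limit reduces to 1 − 0.025^(1/n); with n = 60 this is 0.060.

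| Positive / n | Percent | Exact 95% interval |
|---|---|---|
| 0/60 | 0 | 0 to 6.0% |
| 6/60 | 10 | 3.8 to 20.5% |
| 18/60 | 30 | 18.8 to 43.2% |
| 30/60 | 50 | 36.8 to 63.2% |
| 48/60 | 80 | 67.7 to 89.2% |

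The widest case, 30/60, is (63.2 − 36.8)/2 = 13.2 points either side. Wilson intervals are similar (30/60: 37.7 to 62.3%).

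**Model predictions**

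Inputs from SAP Table 1, estimate with RSE: k64 0.000510 per hour (3.7%), variance 0.432 (11%); k36 0.00362 per hour (7.4%), variance 1.54 (11%); CL 52.0 L/h (1.5%), variance 0.0871; F2 0.0679, variance 0.204 on the logit scale. Regimen: six 300 mg injections (SAP 13.2.6). Assumptions: monthly dosing, reference covariates, uncorrelated parameters, and an LLOQ of 20 pg/mL. The documents give no LLOQ, so 10 to 100 pg/mL is also shown.

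1. More than a year after the last dose, disposition is fast relative to release. The concentration is therefore close to release rate divided by clearance: C(t) ≈ Σ over doses of D(1 − F2) · k36·k64/(k36 − k64) · [exp(−k64·t) − exp(−k36·t)] / CL.
2. Check on the inputs: ln 2/(0.000510 × 24) = 56.6 days, inside the 43 to 60 day half-life range in Protocol 1.2.
3. Month 36 is 36 × 30.4375 × 24 ≈ 26,298 hours, so k64·t ≈ 13.4. An RSE of 3.7% on k64 alone moves a typical subject's concentration by a factor of exp(1.96 × 0.037 × 13.41) = 2.6 in either direction.
4. The share of subjects above LLOQ moves less, because between-subject variation dominates it. Individuals were simulated at the Table 1 estimates, then again over repeated log-normal draws of k64, k36, their variances and CL using the RSEs.

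| Month | Assumed LLOQ | Share above LLOQ | 95% range from parameter uncertainty |
|---|---|---|---|
| 24 | 20 pg/mL | about 30% | 25.5 to 34.1% |
| 36 | 20 pg/mL | about 10.8% | 7.9 to 13.8% |

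Repeat runs differ by a few tenths of a point. At month 36 the point value is about 15% for an assumed LLOQ of 10 pg/mL, 6% for 50 and 3% for 100.

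**The case against.** Descriptive reporting is a defensible choice here. The study has no hypothesis, the primary endpoint is a plot of individual concentrations, and listings and plots will show the raw data. Anyone given a count and a denominator can work out an exact interval, so no information is lost and no estimate becomes wrong. All of that stands, and it limits the point to how precision is presented. It does not rescue the stated reason, and readers of clinical guidance should not have to compute the interval themselves.

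Some stronger readings are tempting but not supported:

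- A reader might infer that the model results will come with no uncertainty at all. They will not: standard errors, precision as a selection criterion, predictive checks and between-subject distributions are all planned. The gap is only that parameter uncertainty is not stated to reach the predicted percentages and times.
- A reader might quote much wider limits by splitting the 12 to 36 month window into bands; 0/15, for example, has an upper limit of 21.8%. SAP 13.1 tabulates by visit and plans no such bands.
- A reader might ask for intervals on every percentage in SAP 13.1. At Part B Visit 1 the combined quantitative UDS result is positive because that is the entry criterion (Protocol 5.4). An interval such as 88.4 to 100% for 30/30 would mean nothing there. At Visits 2 and 3 the group was selected on the same outcome.
- A reader might take the model range as settled. It rests on an LLOQ that the documents do not give, and that assumption moves the answer more than parameter uncertainty does.

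A binomial interval also does not address who was reachable or when in the window each subject was sampled. That is a limit on what the interval shows, and the report should say so.

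**Conclusion.** The point holds in two parts.

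First, the protocol's reason for omitting intervals is not valid and the SAP leaves the omission in place. The Part A Visit 1 percentages will therefore have no stated precision, when the exact 95% interval could be as wide as about 13 points either side with 60 subjects. This rests on the planned number and on assumed observed proportions.

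Second, SAP 13.2.6 does not state that parameter uncertainty is carried into the monthly percentage below LLOQ or the time above LLOQ, although the standard errors will exist. Its size is about 3 points either way at month 36 under the assumed 20 pg/mL LLOQ. That figure ignores correlations and uses the existing model's RSEs; those of the refined model will differ.

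The absence of hypothesis tests is acceptable. This should be changed because it is cheap and bears on the guidance, but it does not invalidate any planned analysis.

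**What to change.** 1. In Protocol 14.1, or through the SAP as that section allows for deviations, replace the sentence with: *No hypothesis tests will be performed.*
2. In SAP 13.1, add exact (Clopper-Pearson) 95% intervals to the positive and negative percentages for FAS Part A at Visit 1. Add a note that they reflect sampling error only, not the availability-limited enrolment or the spread of sampling times. Do not add them to the Part B Visit 1 quantitative UDS results.
3. In SAP 13.2.6, repeat the simulations over draws from the final model's importance-sampling covariance matrix. Report 95% intervals for each monthly percentage below LLOQ and for the percentiles of time above LLOQ, and state the assay LLOQ used.
4. Declare the change in SAP Section 17.

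The cost is SAP wording and a little programming, with no new data, visits or subjects. The drawback is that the reported figures will look less precise.
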